5.3 Pharmacodynamic Assessments

5.3.1 Leg MRI/MRS (Cohorts 1 and 2)

The following leg muscle MRI/MRS parameters will be measured at Baseline and Weeks 12, 24, 36 and 48 during the first 48 weeks and then 6 monthly during the extension phase:

- MRS method
 - Fat Fraction in the Vastus Lateralis (MRS_FF_VL)
 - Fat Fraction in the Soleus (MRS_FF_SOL)

- Water Transverse Relaxation Time (1H2O-T2) in the Vastus Lateralis (MRS _T2_VL)
- Water Transverse Relaxation Time (1H2O-T2) in the Soleus (MRS _T2_SOL)
- 8 point Dixon method
 - Fat Fraction in the Vastus Lateralis (DIX_FF_VL)
 - Fat Fraction in the Soleus (DIX_FF_SOL)
 - Fat Fraction in the Biceps Femoris (DIX_FF_BFLH)
- MRI method
 - Proton Transverse Relaxation Time (T2) in the Vastus Lateralis (MRI_T2_VL)
 - Proton Transverse Relaxation Time (T2) in the Soleus (MRI_T2_SOL)
 - Proton Transverse Relaxation Time (T2) in the Biceps Femoris (MRI_T2_BFLH)

The MRS parameters from the Vastus Lateralis and Soleus are considered the primary MRI/MRS parameters for the study.

The fat fractions are reported as percentages, whilst T2 parameters are reported in ms.

Imputation will not be used for any missing data.

If a subject withdraws from the study prematurely they will also be assessed at the termination visit if not performed in the last 6 weeks.

Changes from baseline will be calculated.

The following velocities of change (change per month) will also be calculated for the MRS fat fraction measurements:

- Baseline to Week 12
- Week 12 to Week 24
- Week 24 to Week 36
- Week 36 to Week 48

And

- Baseline to Week 24
- Week 24 to Week 48

... and so forth when reporting the extension phase data

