9.6 Efficacy Analyses

9.6.1 General

All analyses will be performed on the functional measures population.

Tabulations will be over all Cohorts 1 and 2 subjects and will not provide separate information for the two cohorts. Cohort 3 data will be summarized separately. In addition to the standard set of descriptive statistics summaries will also tabulate the number of subjects where their value has been imputed (see [Section 9.1](#)). The 95% confidence interval will also be included for the mean changes from baseline.

Box and whisker plots will display the Baseline, Weeks 12, 24, 36 and Week 48 data.

Mean changes from baseline, with associated 95% confidence intervals, will be plotted against visit. As visits in the extension phase will be included the plot will also include the n contributing to the visit.

The velocity of change per month will be assessed for specific endpoints. Velocities will be estimated using mixed effect models of the absolute values, including baseline. The model will include visit as a fixed effect term and subject as a random effect term. The following will be estimated along with 95% confidence intervals:

Velocity (12-B): (Week 12 – Baseline)/3

Velocity (24-12): (Week 24 – Week 12)/3

Velocity (36-24): (Week 36 – Week 24)/3

Velocity (48-36): (Week 48 – Week 36)/3

And

Velocity (24-B): (Week 24 – Baseline)/6

Velocity (48-24): (Week 48 – Week 24)/6

...

The following differences between velocities will also be estimated along with 95% confidence intervals:

Velocity (24-12) – Velocity (12-B)

Velocity (36-24) – Velocity (12-B)

Velocity (48-36) – Velocity (12-B)

And

Velocity (48-24) – Velocity (24-B)

...

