9.7 Pharmacodynamics Analyses

9.7.1 Leg MRI/MRS (Cohorts 1 and 2)

All analyses will be performed using the Leg MRI/MRS population.

Tabulations will be over all subjects and will not provide separate information for the different cohorts.

Absolute values and changes from baseline will be summarized by visit for each of the 10 parameters. The 95% confidence interval will also be included for the mean changes from baseline.

The MRS fat fractions for the Vastus Lateralis and Soleus will be summarized by visit using a shift table from baseline. Marginal totals will be included. The categories used will be < 10%, ≥10% and < 20%, ≥ 20% and < 30%, ≥ 30% and < 40%, ≥40% and < 50%, ≥50% and < 60%, ≥60%.

Vastus Lateralis and Soleus MRS fat fraction and T2 parameters

The following outputs will only be presented for the Vastus Lateralis and Soleus MRS fat fraction and T2 parameters.

The velocities of change will be summarized using descriptive statistics. Velocities of change will also be analyzed using the methods described in [Section 9.6.1](#).

Individual subject data will be plotted against age as individual line plots (spaghetti plots) for each parameter.

Box and whisker plots will display the Baseline, Week 12, Week 24, Week 36 and Week 48 data.

Mean changes from baseline, with associated 95% confidence intervals, will be plotted against visit. As visits in the extension phase will be included the plot will also include the n contributing to the visit.

Week 12, 24, 36 and 48 changes from baseline will also be plotted against age on Day 1 and baseline, using different symbols to identify the Week. The Pearson correlation coefficient (for each week) will be footnoted on the plots.

The changes from baseline for parameters will be plotted against one another for Weeks 12, 24, 36 and 48 data. The week will be identifiable using different symbols. The Pearson correlation coefficients (for each week) will also be presented in the footnote of the plots.

The MRS fat fractions will be plotted against the corresponding MRI fat fractions and the MRS T2 values will be plotted against the corresponding MRI T2 values for the Vastus Lateralis and Soleus muscles. Absolute values will be plotted with different symbols used for each visit. The plot will be repeated for changes from baseline.

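### Leg MRS velocities divide changes from Baseline by a fixed 3 or 6 months although the baseline scan may date from Day -28, so steadily rising fat fraction can look like slowing

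*SAP*

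**What the plan says.** SAP 9.6.1 estimates velocities from a mixed model of the absolute values on nominal visit: "The model will include visit as a fixed effect term and subject as a random effect term". Model contrasts are then divided by fixed numbers of months: "Velocity (12-B): (Week 12 – Baseline)/3" and "Velocity (24-B): (Week 24 – Baseline)/6". Later 12-week and 24-week intervals get the same divisors, 3 and 6. Four velocity differences are listed. Three subtract the Baseline-to-Week-12 velocity from a later 3-month velocity, and one subtracts the Baseline-to-Week-24 velocity from the Week-24-to-48 velocity.

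SAP 9.7.1 brings this to the leg: "Velocities of change will also be analyzed using the methods described in" Section 9.6.1, for vastus lateralis and soleus MRS fat fraction and T2. SAP 5.3.1 states: "The MRS parameters from the Vastus Lateralis and Soleus are considered the primary MRI/MRS parameters for the study".

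The descriptive velocities are separate. SAP 5.3.1 says "The following velocities of change (change per month) will also be calculated for the MRS fat fraction measurements" and SAP 9.7.1 says "The velocities of change will be summarized using descriptive statistics". Neither gives a denominator.

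On timing, the protocol's Time and Events Table for Cohorts 1 and 2 has a single pre-dose mark for leg MRI, in the Screening column. The screening and baseline period may begin as early as Day -28 and ends on Day -1. SAP 5.1 takes as baseline the latest available value before first dose, with no limit on its age. It counts the Week 12 and Week 24 targets (Days 84 and 168) from first dose and has no Day 0.

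**The concern.** Post-dose visits are timed from first dose, but the baseline value is timed from whenever the screening scan was done. Any lead between scan and dosing lengthens the first interval and leaves its divisor unchanged. The error goes one way on average: a lead can only lengthen the interval, while the protocol's ±2-week windows for post-dose visits fall on both sides of target.

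Fat fraction is expected to rise in this disease. An over-long first interval therefore inflates the first velocity, and every listed difference subtracts that velocity. In a trial without a control arm, a later velocity below the first is one of the few patterns that could be taken as the disease slowing on treatment. The formula can produce that pattern with an inert drug, and the planned 95% confidence interval would be centred on a biased estimate.

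**Working it through.** **Inputs.** Divisors 3 and 6 (SAP 9.6.1); target Days 84, 168, 252 and 336 and no Day 0 (SAP 5.1); pre-dose scan between Day -28 and Day -1 (protocol Time and Events Table). Assumed: fat fraction rises at a constant rate, there is no drug effect, and post-dose scans are on target.

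**Reproducing the plan's divisors.** Day -1 to Day 84 is 84 days, and 84/28 = 3. Day -1 to Day 168 is 168 days, and 168/28 = 6. The divisors are therefore exact for a Day -1 scan and 28-day months. In calendar months of 30.4375 days they would be 2.76 and 5.52, but that factor is common to all intervals and cancels in the ratios below.

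**General case.** With no Day 0, a scan on Day -L lies 83+L days before Day 84 and 167+L days before Day 168. Set the true rate to 1 per 28 days. Then:

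- V(12-B) = (83+L)/84
- V(24-B) = (167+L)/168
- every later velocity = 1
- apparent slowing = 1 – 1/V

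| Baseline scan | V(12-B) | Slowing, 3-month differences | V(24-B) | Slowing, 6-month difference |
|---|---|---|---|---|
| Day -1 | 84/84 = 1.00 | 0% | 168/168 = 1.00 | 0% |
| Day -7 | 90/84 = 1.07 | 6.7% | 174/168 = 1.04 | 3.4% |
| Day -14 | 97/84 = 1.15 | 13.4% | 181/168 = 1.08 | 7.2% |
| Day -21 | 104/84 = 1.24 | 19.2% | 188/168 = 1.12 | 10.6% |
| Day -28 | 111/84 = 1.32 | 24.3% | 195/168 = 1.16 | 13.8% |

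If scan days were spread evenly over Day -28 to Day -1 (an assumption), mean L is 14.5. Then V(12-B) = 97.5/84 = 1.16 and V(24-B) = 181.5/168 = 1.08, with slowing of 13.8% and 7.4%.

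**Check with the planned model.** One hundred simulated trials of 40 boys, with evenly spread scan days, post-dose visits within ±14 days of target, visit fixed and subject random, gave V(12-B) = 1.16 against 1.00 to 1.01 for the later 3-month velocities. The 3-month differences were -0.14 to -0.16 and the 6-month difference was -0.07.

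**Check of the remedy.** A second simulation used 4,000 trials of 40 boys with complete data, visits within ±14 days, mean rate 1 per 28 days, rate SD 0.5 and residual SD 1 (all assumed). Fixed divisors gave a Week 24-12 difference of -0.152 with all scans on Day -14 and -0.322 with all on Day -28 (closed form -0.155 and -0.321). Subject-level velocities on actual dates put all four differences within 0.003 of zero at every lead examined, with t-based interval coverage of 94.6% to 95.6%.

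**The case against.** The case for leaving this alone has real content.

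- **The size is unknown.** Day -28 is a ceiling, and scans on Day -1 would give no bias. This stands. The protocol's aim of balancing boys by fat:water fraction (Section 5.1) suggests that scans are read before enrolment, but that is an inference.
- **Progression may not be linear.** Acceleration would offset the artefact and deceleration would add to it. This also stands, though it does not justify equal divisors for unequal intervals.
- **The analysis carries little formal weight.** Velocity differences appear in no objective or endpoint, the study is not powered, and both terms of each difference are mainly on-treatment time. This limits the importance of the point but does not remove the bias.
- **The lead would be visible.** SAP 9.1 lists study days, SAP 9.7.1 plots individual data against age, and the later velocities, which do not use the baseline scan, are reported on their own. None of this corrects the listed differences.

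A reader might infer that the confidence intervals would often wrongly exclude zero. The documents do not support a figure. With only a random intercept, variation in slope between boys enters the residual and widens the interval. Trial calculations under the planned model ranged from about 0% to 58%, depending on the assumed slope SD and lead, and the documents give neither a progression rate nor an SD.

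**Conclusion.** The point holds for the model-based leg MRS fat fraction velocities and should be fixed. Under constant accumulation and on-target post-dose scans, the apparent slowing runs from 0% (Day -1) to at most 24.3% in the 3-month differences and 13.8% in the 6-month difference (Day -28). The mechanism is certain; its size in this trial depends on scan dates that the documents do not give.

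Three wider readings are not supported:

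- The direction does not carry over to T2, for which the documents show no rising trend.
- The primary endpoint is not biased in the drug's favour. For change from baseline, the same lead adds untreated worsening and counts against the drug.
- The descriptive velocities cannot be said to share the error. Their denominator is unstated and could be actual time.

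**What to change.** For the leg MRS velocities, state in SAP 5.3.1 and 9.7.1 that each descriptive velocity is the change divided by the days between the two scan dates, converted with a stated month length (28 or 30.4375 days). Replace the fixed-divisor model estimates by one of these:

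- means of the subject-level velocities and of their differences, with t-based 95% confidence intervals; or
- a mixed model with piecewise-linear time in actual days from first dose, which yields a slope for each interval.

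Compute elapsed time from calendar dates, because subtracting study-day numbers across Day 1 overcounts by one. Report the distribution of the interval from baseline scan to first dose, and say that the first velocity still includes some pre-dose time.

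The cost is SAP wording and a little programming; the dates are already due to be listed. The subject-level option uses only boys with every scan that a difference needs, whereas the planned model uses all available values. The piecewise option avoids that loss but was not simulated here.

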9.6.2 Six-Minute Walk Distance

Screening and baseline data will be plotted using a Bland-Altman plot to assess their agreement for both the 6MWD and the %-predicted 6MWD. If there is agreement between the two measurements the average will be used as baseline for other analyses; otherwise the last measurement prior to dosing will be used. Note: These data have been reviewed and the decision was taken to use the last measurement before dosing.

Observed values and changes from baseline will be summarized by visit using descriptive statistics for both the 6MWD and the %-predicted 6MWD.

The number and percentage of subjects using orthoses or aids will be summarized by visit using a shift table from baseline. Marginal totals will be included. Similarly, the number and percentage of subjects having falls or having the follower providing support will be summarized using a shift table.

The velocities of change will be summarized using descriptive statistics. Velocities of change will also be analyzed using the methods described in [Section 9.6.1](#).

Individual subject data will be plotted against age as individual line plots (spaghetti plots).

Week 12, 24, 36 and 48 changes from baseline will also be plotted against age on Day 1 and baseline, using different symbols to identify the Week. The Pearson correlation coefficient (for each week) will be footnoted on the plots.

The time till a 10% reduction in 6MWD will be plotted using a Kaplan-Meier curve and estimated proportions will be tabulated over time.

9.6.3 North Star Ambulatory Assessment

Scores and changes from baseline will be summarized by visit using descriptive statistics for both the total score and the linearized score.

The individual activity scores will be summarized by visit using a shift table from baseline. Marginal totals will be included.

The number (percentage) of subjects who have lost 0, 1, 2...activities will be tabulated by visit.

The velocities of change for the total score will be summarized using descriptive statistics. Velocities of change will also be analyzed using the methods described in [Section 9.6.1](#).

The 6MWD and NSAA total score changes from baseline will be plotted together against visit in trellis plots with one subject per plot. The two parameters will have different y-axes and a legend will be provided to distinguish 6MWD and NSAA lines on the plot.

Individual subject total scores will be plotted against age as individual line plots (spaghetti plots).

Week 12, 24, 36 and 48 changes from baseline for the total scores will also be plotted against age on Day 1 and baseline, using different symbols to identify the Week. The Pearson correlation coefficient (for each week) will be footnoted on the plots.

The box and whisker and mean change from baseline plots will only be presented for the total scores.

The number and percentage of subjects who lose ambulation will be summarized by visit.

9.6.4 10-Metre Run/Walk

Scores and changes from baseline will be summarized by visit using descriptive statistics.

The velocities of change will be summarized using descriptive statistics. Velocities of change will also be analyzed using the methods described in [Section 9.6.1](#).

Individual subject data will be plotted against age as individual line plots (spaghetti plots).

Week 12, 24, 36 and Week 48 changes from baseline will also be plotted against age on Day 1 and baseline, using different symbols to identify the Week. The Pearson correlation coefficient (for each week) will be footnoted on the plots.

9.6.5 Time to Stand

Scores and changes from baseline will be summarized by visit using descriptive statistics.

The velocities of change will be summarized using descriptive statistics. Velocities of change will also be analyzed using the methods described in [Section 9.6.1](#).

Individual subject data will be plotted against age as individual line plots (spaghetti plots).

Week 12, 24, 36 and Week 48 changes from baseline will also be plotted against age on Day 1 and baseline, using different symbols to identify the Week. The Pearson correlation coefficient (for each week) will be footnoted on the plots.

9.6.6 PODCI

Scores and changes from baseline will be summarized by visit using descriptive statistics for each scale's standardized score and the global functioning scale score.

Individual subject global function scale score data will be plotted against age as individual line plots (spaghetti plots).

The box and whisker and mean change from baseline plots will only be presented for the global functioning scale score.

9.6.7 PUL

Scores and changes from baseline will be summarized by visit using descriptive statistics for each dimension and the total score.

Individual subject total score data will be plotted against age as individual line plots (spaghetti plots).

Week 12, 24, 36 and Week 48 changes from baseline in the total score will also be plotted against age on Day 1 and baseline, using different symbols to identify the Week. The Pearson correlation coefficient (for each week) will be footnoted on the plots.

9.7 Pharmacodynamics Analyses

9.7.1 Leg MRI/MRS (Cohorts 1 and 2)

All analyses will be performed using the Leg MRI/MRS population.

Tabulations will be over all subjects and will not provide separate information for the different cohorts.

Absolute values and changes from baseline will be summarized by visit for each of the 10 parameters. The 95% confidence interval will also be included for the mean changes from baseline.

The MRS fat fractions for the Vastus Lateralis and Soleus will be summarized by visit using a shift table from baseline. Marginal totals will be included. The categories used will be < 10%, ≥10% and < 20%, ≥ 20% and < 30%, ≥ 30% and < 40%, ≥40% and < 50%, ≥50% and < 60%, ≥60%.

Vastus Lateralis and Soleus MRS fat fraction and T2 parameters

The following outputs will only be presented for the Vastus Lateralis and Soleus MRS fat fraction and T2 parameters.

The velocities of change will be summarized using descriptive statistics. Velocities of change will also be analyzed using the methods described in [Section 9.6.1](#).

Individual subject data will be plotted against age as individual line plots (spaghetti plots) for each parameter.

Box and whisker plots will display the Baseline, Week 12, Week 24, Week 36 and Week 48 data.

Mean changes from baseline, with associated 95% confidence intervals, will be plotted against visit. As visits in the extension phase will be included the plot will also include the n contributing to the visit.

Week 12, 24, 36 and 48 changes from baseline will also be plotted against age on Day 1 and baseline, using different symbols to identify the Week. The Pearson correlation coefficient (for each week) will be footnoted on the plots.

The changes from baseline for parameters will be plotted against one another for Weeks 12, 24, 36 and 48 data. The week will be identifiable using different symbols. The Pearson correlation coefficients (for each week) will also be presented in the footnote of the plots.

The MRS fat fractions will be plotted against the corresponding MRI fat fractions and the MRS T2 values will be plotted against the corresponding MRI T2 values for the Vastus Lateralis and Soleus muscles. Absolute values will be plotted with different symbols used for each visit. The plot will be repeated for changes from baseline.

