In the meantime, a reformulation Phase 1b study (SMT C11004) in DMD patients demonstrated that a powder for oral suspension (F6), markedly increased exposure. In Study SMT C11004 two newly developed formulations, (a nanosuspension (F5) and a powder for oral suspension (F6)), were administered orally to determine safety and pharmacokinetics in healthy volunteers. Both formulations were found to be safe and well tolerated in the healthy volunteers though transient elevations in liver function tests were seen, the significance of which is unknown. Based on review of the safety, tolerability and pharmacokinetic data, the powder for oral suspension formulation (F6) was chosen to have its safety and pharmacokinetics investigated in DMD patients. The F6 formulation was administered to the DMD boys at doses of 0.25 g *bid*, 0.5 g *bid* and 1 g *bid*. Based upon the safety, tolerability and favourable pharmacokinetics a 1 g *bid* dose of the F6 formulation was chosen to be administered in Study SMT C11005, in a separate cohort of approximately 10 patients (Cohort 2).

PhaseOut DMD (this open label Phase 2 trial) will include both the original formulation (F3) and the new formulation (F6) each with a modified diet. Each formulation is likely to exhibit different plasma concentration ranges which together with safety and pharmacodynamic data will aid in the selection of the preferred formulation and dose for future studies. By using both the F3 and F6 formulation in this study and allowing all patients with DMD irrespective of their SMT C1100 exposure levels to participate in this study, a wide concentration response range can be investigated, which will help to identify the range of SMT C1100 plasma levels that may modulate utrophin muscle levels sufficiently to provide therapeutic benefit. This will facilitate the design of future studies.

Study Number: SMT C11005	Compound No.: SMT C1100
Protocol	Version: 5.0 24Feb2017

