Study Number: SMT C11005	Compound No.: SMT C1100
Protocol	Version: 5.0 24Feb2017

The potential of SMT C1100 to induce utrophin modulation in primary human skeletal muscle cells (myotubes) was assessed in the utrophin induction assay (Study No. N-058). SMT C1100 was shown to trigger utrophin protein modulation in a dose-dependent manner with a maximal 1.45-fold increase and the EC₅₀ was determined to be 205 nM (67 ng/mL). In SMT C11004 Part B, at the two highest dose levels, mean (geometric) SMT C1100 C_{max} was > 70 ng/mL, with the highest geometric mean C_{max} over 24 hours being 390 ng/mL at the 1 g *bid* dose level at steady state (Day 7). In study N-115, DHD III has also shown potential to modulate utrophin transcription in the H2K cell reporter assay with 6-fold lower potency (EC₅₀ ~4.5 μM) compared to SMT C1100. Thus the relatively high levels of DHD III metabolite (mean C_{max} of 14 μM at steady state) may provide a meaningful contribution to pharmacology. DHD I was much less potent in the reporter assay- 30-fold lower than SMT C1100 - and plasma exposure is also lower than DHD III so the DHD I metabolite is less likely to play a key role in pharmacology.

In Study SMT C11004, overall there was an increase in steady state SMT C1100 C_{max} and AUC₀₋₂₄ with increasing dose which was greater than dose proportional at doses of 0.5 g *bid* and 1 g *bid* for 7 days. There was little to no accumulation of SMT C1100 with repeated dosing. There was dose proportionality between the 0.25 g *bid* and 0.5 g *bid* dose levels. The F6 powder for oral suspension at a dose of 1 g *bid* achieved a greater than six-fold increase in maximum SMT C1100 plasma levels (14-fold if comparing dose normalised data) in DMD patients compared to those achieved with the current clinical formulation, F3, and consequently this formulation and dose will be investigated in a small number of patients in Study SMT C11005.

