12.1.2. Treatment Comparisons

Though the study includes a single treatment group, comparisons will be made with SMT C1100 plasma exposure and MRI parameters and other endpoints through concentration response analyses. Similarly, the relationship between utrophin expression and other endpoints will be explored.

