12.1.4. Key Elements of Analysis Plan

Where appropriate the data from the different cohorts will be pooled for analyses. Baseline characteristics will be summarised for each cohort separately and over all patients.

Changes from baseline in primary and secondary endpoints will be summarised and plotted by visit, as will blood biomarker data and pharmacokinetic data. In addition to descriptive statistics (n, mean, standard deviation, median, minimum and maximum) data will be summarised categorically through the count of patients with specific levels of improvement or deterioration from baseline with the different endpoints.

Data for sub-groups based on baseline characteristics, SMT C1100 concentrations and utrophin expression will also be summarised.

Study Number: SMT C11005	Compound No.: SMT C1100
Protocol	Version: 5.0 24Feb2017

If possible, changes from baseline may be compared with historical control data.

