Section 5 provides details of where efficacy data is imputed if the reason given for not performing or completing an assessment is related to the subject's medical condition (e.g. if a subject is physically unable to do the 6MWD then their distance will be imputed as 0). For such efficacy endpoints the number of imputed values will also be tabulated along with other descriptive statistics in summary tables.

Listings will present cohort as a sub-header. Unless otherwise specified, tabulations will present data for each cohort separately as well as all subjects.

In by-time summary tables the baseline will be summarized using all available data, but also for each visit using only the baseline data from subjects with available data at the visit; hence the mean change from baseline will equal the mean visit value – mean baseline value.

All data will be listed and will present study days in addition to dates. Dates will be presented in DDMMYY format (e.g. 28Jul2017).

Listings will be sorted by cohort (used as sub-header), subject and, where appropriate, time.

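### Functional, leg MRI/MRS and biopsy tables pool F3 2.5 g bid and F6 1 g bid without by-cohort columns, against the SAP's own default and without a reason, so a change confined to F6 can be masked

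*SAP*

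**What the plan says.** SAP 9.1 sets the general rule: "Unless otherwise specified, tabulations will present data for each cohort separately as well as all subjects". Three sections then depart from it:

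- SAP 9.6.1 (all functional endpoints): "Tabulations will be over all Cohorts 1 and 2 subjects and will not provide separate information for the two cohorts". Cohort 3 is summarised separately.
- SAP 9.7.1 (leg MRI/MRS, the primary endpoint): "Tabulations will be over all subjects and will not provide separate information for the different cohorts".
- SAP 9.7.3 (biopsy: utrophin, MHCd, fibre diameter and pathology): the same sentence as in 9.7.1.

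None of the three gives a reason. SAP section 10, which lists changes from the protocol's planned analyses, does not mention the pooling of Cohorts 1 and 2. Protocol 12.1.4 allows pooling with a qualifier: "Where appropriate the data from the different cohorts will be pooled for analyses".

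The two cohorts receive different products at different doses: F3 2.5 g bid in Cohort 1 and F6 1 g bid in Cohort 2 (SAP 3.0). Protocol 8.2 reports that F6 at 1 g bid gave a "greater than six-fold increase in maximum SMT C1100 plasma levels" compared with F3 in boys with DMD. The Rationale in the Protocol Summary says that each formulation's concentration range, taken with safety and pharmacodynamic data, "will aid in the selection of the preferred formulation and dose for future studies".

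**The concern.** The rationale lists three kinds of evidence for choosing between formulations: concentrations, safety and pharmacodynamics. The SAP tabulates the first two by cohort. For the MRI/MRS and biopsy data, which are the main pharmacodynamic evidence, and for function, it removes the cohort columns that its own default would have produced.

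The pooled mean is weighted three to one towards F3. A change seen only in the smaller, higher-exposure cohort is diluted to a quarter of its size, and the mixture of two means widens the interval. A reader of the tables could not tell such a result from no change in either cohort. Nor could a pooled change, if one were seen, be traced to a formulation.

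**Working it through.** **No figure to reproduce.** The sample size is not based on power, and the documents give no SD or effect size. Everything below is in units of the within-cohort SD of the change from baseline. I assume equal SDs, complete data, approximate normality and a two-sided 95% interval.

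**Inputs.** Cohort 1 n = 30, Cohort 2 n = 10 (SAP 3.0). Second biopsies (Protocol 4.1.1): Cohort 1 has 8 + 22/2 = 19 at Week 24 and 11 at Week 48; Cohort 2 has 6 and 4. SAP 9.7.3.1 analyses the two weeks separately.

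**Weights.** 30/40 = 0.75 for F3 and 10/40 = 0.25 for F6. Illustrative scenario: F6 shifts the endpoint by 1 SD and F3 shows zero change.

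**Pooled result, MRI/MRS or function (n = 40).**
- Mean = 0.25 × 1 = 0.25 SD.
- SD of the mixture = √(1 + 0.75 × 0.25 × 1²) = √1.1875 = 1.09.
- Half-width = t(39) × 1.09/√40 = 2.023 × 1.09/6.325 = 0.35 SD. If the two cohort means were equal it would be 0.32 SD.
- Chance that the interval excludes zero: non-central t, 39 df, non-centrality 0.25 × √40/1.09 = 1.45, which gives 29%. A simulation with exactly 30 and 10 boys gives 28%.

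**Cohort 2 alone (n = 10).**
- Half-width = t(9)/√10 = 2.262/3.162 = 0.72 SD.
- Non-centrality √10 = 3.16, 9 df, which gives 80%.

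**Cohort 2 biopsies, same 1 SD shift.**

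| Visit | n | Half-width | Excludes zero |
|---|---|---|---|
| Week 24 | 6 | 2.571/√6 = 1.05 SD | 51% |
| Week 48 | 4 | 3.182/√4 = 1.59 SD | 29% |

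**Sensitivity to the assumed shift.** At 0.5 SD, Cohort 2 alone (n = 10) excludes zero in about 29% of trials. The pooled mean is then 0.125 SD and the mixture SD is √(1 + 0.1875 × 0.25) = 1.02. The non-centrality is 0.125 × √40/1.02 = 0.77, which gives about 12%.

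**What by-cohort columns could say about F6 minus F3.**
- MRI/MRS or function (30 and 10): half-width = t(38) × √(1/30 + 1/10) = 2.024 × 0.365 = 0.74 SD. With 20% dropout (24 and 8) it is 0.83 SD.
- Biopsy: 0.97 SD at Week 24 (19 and 6) and 1.26 SD at Week 48 (11 and 4).
- A true difference of about 1.02 SD would be needed for 80% power with 30 and 10 boys (normal approximation).

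**Whether cohort information survives elsewhere.**
- Pharmacokinetics are summarised by cohort (SAP 9.9).
- Safety, baseline, blood biomarker and pulmonary tables follow the 9.1 default, because no exception is stated.
- Listings are by cohort: "Listings will be sorted by cohort (used as sub-header), subject and, where appropriate, time".
- SAP 9.10.1 plots MRS, biopsy and functional changes against exposure. It specifies no cohort symbol, although 9.9 requires the individual concentration plots to identify cohort.
- The velocity models (SAP 9.6.1) have visit as the only fixed effect, and the biopsy models (9.7.3) likewise carry no cohort term.

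**The case against.** The strongest case for the plan is that pooling follows from the design. The protocol permits it where appropriate and asks for by-cohort summaries only of baseline characteristics (12.1.4) and pharmacokinetics (12.1.4.2). Protocol 12.1.2 opens with "Though the study includes a single treatment group" and makes concentration-response the comparison. Both formulations were included to widen the exposure range, and earlier studies found high between-patient variability in exposure, so individual exposure may separate boys better than cohort does. SAP 9.10.1 supplies those plots. Formulation choice appears in the rationale and is not a primary, secondary or exploratory objective. The individual data remain in the listings by cohort.

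Most of this stands as context, but it does not justify leaving the columns out. Listings give no mean or interval by formulation. In unmarked exposure plots, with a more than six-fold gap in earlier maximum levels, a pooled correlation may partly reflect cohort (formulation, dose or country), and the reader could not see it. Protocol 12.1.4 also plans summaries for sub-groups by concentration and utrophin expression; I find none in the SAP. Small numbers call for wide intervals labelled as descriptive, and the SAP already tabulates safety for a cohort of about 10.

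A reader might infer that the missing columns are why the trial cannot show which formulation works. The documents do not support that. The study has no randomisation, no concurrent control and no powering. Cohort 2 is US-only while Cohort 1 is UK and US, and dose changes together with formulation. By-cohort columns would not show it either.

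**Conclusion.** The SAP omits by-cohort summaries for the functional, primary leg MRI/MRS and biopsy endpoints, against its own default and without a reason. The tables therefore lack the pharmacodynamic results by formulation that the protocol rationale relies on, and they can mask a change confined to F6. In the 1 SD illustration, detection of a non-zero change falls from about 80% in Cohort 2 alone to about 29% pooled. For biopsies, Cohort 2 alone reaches only about 51% (Week 24) and 29% (Week 48).

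These percentages rest on the assumed shift, equal SDs, complete data and zero change on F3. The last is a convenience: DMD is progressive, so an untreated boy need not show zero change, and an interval that excludes zero does not show that a formulation works.

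This is a reporting weakness in an exploratory study. It does not invalidate the pooled analysis. It should be corrected because the correction needs no new data.

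**What to change.** 1. In SAP 9.6.1, 9.7.1 and 9.7.3, replace the pooling sentence with: *Tables will present Cohort 1, Cohort 2 and Cohorts 1+2, with 95% CIs for mean change.* Keep Cohort 3 separate in 9.6.1.
2. In all SAP 9.10 relationship plots, identify cohort by symbol.
3. State that by-cohort results are descriptive, because the cohorts are non-randomised and confounded with country and dose, and that no formal formulation comparison is intended.
4. Optionally, add cohort and cohort-by-visit terms in a supportive version of the MRI/MRS and functional velocity models. Do not add them to the biopsy models, where the Cohort 2 estimate would rest on 6 or 4 boys.

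The cost is extra table columns and a plot symbol, plus two model terms if item 4 is taken up. Cohort 2 intervals will be wide: about ±0.72 SD for MRI/MRS and function, and wider for biopsies.
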